### **Study Aims and Hypotheses**

The goals of the study will be as follows:

- 1. To examine the perceived acceptability, usefulness, and client satisfaction following participation in the Single-Session Consultation (SSC) service at the Krasner Psychological Center (KPC) and Mind Body Clinical Research Center (MBCRC) among waitlisted adolescent and adult clients
- 2. To examine therapists' perceived acceptability, feasibility, and effectiveness of the single session consultation at three time points: pre-training, post-training, and post-SCC administration
- 3. To assess the demand for and feasibility of providing the SSC service at the Krasner Psychological Center and Mind Body Clinical Research Center (i.e., documenting the proportion of clients who choose to participate in the service when it is offered; documenting the number of sessions successfully completed, rescheduled, and/or cancelled).
- 4. To assess whether levels of proximal clinical outcomes (e,g, hope, agency) are improved immediately following completion of the SSC, both in adolescent and adult clients.
- 5. To assess whether levels of psychological symptoms are improved two weeks following completion of the SSC, both in adolescent and adult clients.
- 6. To assess rates of (a) remaining on the clinic waitlist for therapy and (b) length of subsequent treatment at the Mind Body Clinical Research Center and Krasner Psychological Center among individuals participating in the SSC, relative to clients who sought out services in the six months prior to the SSC being offered to clients (January June 2019).

Hypotheses associated with each of these aims will be as follows:

- 1. Clients' proximal clinical outcomes (e,g, hope, measured by the Beck Hopelessness Scale 4 item version, and Agency, measured by the State Hope Scale; both primary study outcomes), which are hypothesized to serve as mechanisms for intervention effects, will improve from immediately pre-SSC completion to immediately post-SSC.
- 2. Adolescent and adult clients will perceive the SSC at the Mind Body Clinical Research Center and Krasner Psychological Center as acceptable and useful in addressing their clinical needs, indexed by mean ratings of at least 3.5 out of 5 across the five items on the "Consultation Feedback Form".
- 3. The SSC will show feasibility as a model for service provision at the Mind Body Clinical Research Center and Krasner Psychological Center (i.e., a majority [>50%] of clients who are offered the SSC service will elect to receive it, and most [>75%] of clients who schedule an SSC appointment will attend)
- 4. Clients' overall psychological symptom levels will reduce two weeks after the SSC, relative to symptoms immediately prior to the SSC

- 5. No prediction is made about therapists' perceived acceptability, feasibility, and effectiveness of single session interventions at baseline or their subsequent assessment, given the novelty of research in this domain.
- 6. Clients who receive the SSC will be less likely to remain on the clinic wait list—and, among those who elect to remain on the clinic wait list, total therapy duration will be briefer—relative to clients who sought service at the Mind Body Clinical Research Center and Krasner Psychological Center prior to the SSC service being offered.

Note that data will be available for testing hypotheses 1-5 substantially sooner than for testing hypothesis 6, as the duration of clients' potential future psychotherapy at the Krasner Psychological Center and Mind Body Clinical Research Center is impossible to determine. Whereas data for the first four hypotheses will be available two weeks subsequent to recruitment completion, data for the fifth hypothesis may be unavailable for up to a year subsequent to recruitment completion. Accordingly, the authors may report results from hypotheses 1-5 in a manuscript or conference presentation prior to completion of data collection for hypothesis 6, noting that data relevant to hypothesis 6 will be reported at a to-be-determined future date. Data relevant to hypothesis 6 (which requires extraction of aggregate client information associated with previous Mind Body Clinical Research Center and Krasner Psychological Center clients) will not be collected, and thus will remain unknown to investigators, until all relevant data are available for analysis (i.e., until all clients who completed the SSC and chose to receive full-length psychotherapy have terminated their course of treatment at the clinic).

# **Sample Size Justification**

We are primarily interested in obtaining precise estimates of feasibility and acceptability outcomes; client satisfaction ratings; and changes in possible change mechanisms (hope, agency), which will aid in the planning of a larger-scale efficacy trial. A client sample size of 40 from two outpatient sites will allow us to be relatively precise in our conclusions regarding feasibility outcomes, as well as change in hope and agency scores from pre-to-post-intervention, based on guidelines for pilot study planning proposed by Joulius (2005) and Whitehead et al (2016).

We will also recruit therapists to take part in this study. Specifically, all therapists attending the initial training will be offered the opportunity to voluntarily and anonymously complete a questionnaire on their perceptions of the single-session consultation program. Since we have no way of knowing how many therapists will choose to participate in this study, the sample size for therapist participants is unknown. Therapist data will be exploratory, serving as pilot data for potential future studies.

Note: the trial initially recruited three outpatient centers (Krasner Psychological Center, Mind Body Clinical Research Center, and Child Adolescent Outpatient Services). Due to logistical and administrative issues encountered at the Child Adolescent Outpatient Services during study set up, this site was excluded. Based on the ongoing recruitment rates at the two remaining sites, the sample size of 40 is feasible to recruit.

## **Analytic Plan**

To address Hypothesis 1, we will conduct two 2-tailed paired samples t-tests to assess whether participants scores on the Beck Hopelessness Scale – 4 item version and the State Hope Scale, respectively, significantly reduced from pre-SSC to post-SSC. A pre-post difference with a p value of < .05 will indicate a significant change in hope, agency, from pre-SSC to post-SSC. To address Hypothesis 2, we will examine mean scores on the "Consultation Feedback Form," which contains 5 items rated on a 1-5 Likert scale by participants (e.g., "Did you find the consultation helpful in addressing your concern(s)?"; "How motivated do you feel to use your action plan?") A mean score of 3.5 out of 5 or higher across participants in this study would indicate participants found the SSC more than somewhat helpful in addressing their concerns.

To address Hypothesis 3, we will first divide the number of people who accepted the Mind Body Clinical Research Center and Krasner Psychological Center's invitation to take part in the SSC service (whether or not they subsequently attend their scheduled session) by the number of people who declined the invitation to take part in the SSC service. We will then divide the number of people who attended their scheduled SSC session by the total number of people who scheduled an SSC session, regardless of future attendance. If the first number exceeds .5 (50%), and the second number exceeds .75 (75%), we will conclude the SSC's feasibility as a service delivery model.

To address Hypothesis 4, we will again use a 2-tailed paired samples t-test to assess whether participants' brief symptom inventory score significantly reduced from pre-SSC to follow-up. A pre to follow-up difference with a p value of < .05 will indicate a significant change.

To address our fifth research question (for which no hypotheses are proposed), we will aggregate descriptive statistics from the "Therapist Beliefs about SSC" scales and will compare the scales between (1) pre-training and post-training and (2) post-training and post-SSC administration. Positive perceptions of the SSC at any given time-point will be defined by a mean rating of at least 3.5 out of 5 across all items; less-than-positive perceptions will be defined by a mean rating of less than 3.5 out of 5 across all Likert scale-rated items. We will report all qualitative data collected via this measure—specifically, we will report therapists' written responses to openended questions about their perceptions of the SSC. Because the scope and amount of this qualitative data are likely to be limited, and given the exploratory nature of the present study, we do not intend to conduct any formal qualitative data analyses in this study.

To address Hypothesis 6, we will conduct two 2-tailed independent-samples t tests. First, we will assess whether the percentage of individuals removing themselves from the clinic's waitlist after completing the SSC differs from the percentage of individual who had removed themselves from the waitlist in the six months prior to the SSC's being offered at the clinic. A difference with a p value of < .05, with a higher value for the SSC group, would suggest that individuals who receive the SSC may be more likely to voluntarily remove themselves from the clinic waitlist than individuals who had not received the SSC in the past. Second, we will calculate the mean number of psychotherapy sessions completed at the Mind Body Research Clinical Center and Krasner Psychological Center among individuals who receive the SSC and elect to remain on the clinic's waitlist. We will then test whether this mean number of sessions differs from the mean

number of sessions completed by clients who began psychotherapy in the six months prior to the SSC's being offered at the clinic. A difference with a p value of < .05, with a lower value for the SSC group, would suggest that individuals who receive the SSC may be more likely to have a shorter course of psychotherapy than those who do not receive the SSC prior to full-length treatment. Note that for both of our Hypothesis 6 analyses, we will restrict our sample of previously-seen clients to those in the same age-range as in the study sample, in order to optimize comparability between groups.

We will use maximum likelihood estimation to address any item- and subject-level missing data that may emerge.

The false discovery rate (FDR) will be applied to identify potential false-positive results. Q-values will be computed for p-values from t tests using an online calculator applying Benjamini and Hochberg's (1995) approach (https://www.sdmproject.com/utilities/?show=FDR). Results will be considered significant if FDR corrected q < 0.05 (incurring maximum 5% false-positive rate amongst all tests meeting significance at p < 0.05). Both p and q values will be reported.

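### Hypothesis 3 uptake is computed as accepted over declined but judged against a 50% proportion, so uptake just above one third passes the uptake half of the feasibility rule

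*SAP*

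**What the plan says.** Three places in the SAP deal with uptake.

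- **Study Aims and Hypotheses, Aim 3** describes the demand measure as "documenting the proportion of clients who choose to participate in the service when it is offered".
- **Study Aims and Hypotheses, Hypothesis 3** sets the criterion: "a majority [>50%] of clients who are offered the SSC service will elect to receive it".
- **Analytic Plan, Hypothesis 3** gives the calculation. The numerator is the acceptors: "we will first divide the number of people who accepted the Mind Body Clinical Research Center" and Krasner Psychological Center invitation, whether or not they later attend. The division is then "by the number of people who declined the invitation to take part in the SSC service".

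The same paragraph defines attendance as attenders divided "by the total number of people who scheduled an SSC session, regardless of future attendance". Feasibility is concluded if the first number is above .5, written there also as 50%, and the second is above .75.

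**The concern.** The aim and the hypothesis both use clients offered the service as the denominator. The calculation uses only those who declined. That turns a proportion into an odds, while the threshold and its percentage gloss remain those of a proportion. The attendance measure in the same paragraph does use a total as its denominator, so the uptake measure also breaks the plan's own pattern.

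The Sample Size Justification lists feasibility among the outcomes of primary interest and says the estimates will help plan a larger efficacy trial. Followed literally, the plan would treat the majority criterion as met when just under two thirds of those who answered had refused the service. An analyst could defend either calculation from the text, and the two give opposite answers on uptake over a wide range.

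**Working it through.** **Inputs from the SAP.** A = number accepting; D = number declining; uptake threshold 0.5; planned client sample 40 ("A client sample size of 40 from two outpatient sites"), used below for illustration only.

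**Assumed inputs.** The number of clients offered the SSC, N, is not stated; 60 to 120 is taken. Non-response shares of 20% and 30% are scenarios.

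**1. Odds to proportion.** If everyone offered either accepts or declines, the ratio is o = A/D and uptake is p = A/(A+D) = o/(1+o).

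- Rule as written: o > 0.5 gives p > 0.5/1.5 = 33.3%. This does not reproduce the 50% criterion.
- Hypothesis 3: p > 0.5 corresponds to o > 0.5/0.5 = 1.0.

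This step is algebra and does not depend on N.

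**2. Illustration with 40 acceptors.**

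- As written, up to 79 decliners pass: 40/79 = 0.506, and uptake is 40/119 = 33.6%.
- Under the stated criterion, at most 39 decliners pass: uptake is 40/79 = 50.6%.

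**3. Chance of passing the uptake criterion.** Exact binomial tails with every client offered giving an answer. The minimum passing count is the smallest A with A/(N−A) > 0.5 (written) or A/N > 0.5 (stated).

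| N offered (assumed) | Minimum A, written | Minimum A, stated | P(pass) at 40% uptake, written | P(pass) at 40% uptake, stated |
|---|---|---|---|---|
| 60 | 21 | 31 | 0.82 | 0.04 |
| 80 | 27 | 41 | 0.90 | 0.03 |
| 100 | 34 | 51 | 0.91 | 0.02 |
| 120 | 41 | 61 | 0.92 | 0.01 |

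At 35% true uptake with N = 80, the probabilities are 0.63 (written) and 0.002 (stated).

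**4. Non-response.** If a share r of those offered never answers, then A + D = (1−r)N and the written rule needs A > (1−r)N/3. The bar among all offered is (1−r)/3: 0.80/3 = 26.7% at r = 20%, and 0.70/3 = 23.3% at r = 30%. As a worked case, 40 accept, 79 decline and 20 do not answer: A/D = 0.506 passes, while uptake among all offered is 40/139 = 28.8%.

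**The case against.** The strongest reply is that the intent is plain. The aim, the hypothesis and the percentage gloss all point to a proportion, so this looks like a denominator slip that a sensible analyst would correct, and a reader given the counts could recompute uptake. That is fair as to intent. It does not settle the matter, because the Analytic Plan is the operational text and nothing elsewhere in the SAP overrides it.

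Second, feasibility needs both criteria, so low uptake alone does not produce a feasibility conclusion, and the probabilities above concern the uptake half only. This stands. As an illustration, with 32 schedulers (40% of 80) and an assumed true attendance of 80%, the attendance criterion passes with probability about 0.70, so the joint chance as written is about 0.90 × 0.70 = 0.63. Under the stated uptake rule the joint chance cannot exceed 0.03. The joint condition lowers the risk but does not remove the error.

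Third, hope and agency are the named primary outcomes, and no significance test or sample size figure uses this ratio. The SAP also ties no formal progression decision to the rule. These points are correct and limit the reach of the error to the feasibility conclusion.

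Finally, the number offered and the non-response shares are assumed. The 33.3% equivalence needs neither.

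**Conclusion.** The concern holds, and the rule must be corrected. As written, the effective uptake bar is anything above 33.3% of those who answered, instead of more than 50% of those offered. If every client offered answers, the written rule gives the wrong answer on the majority criterion whenever observed uptake lies above one third and does not exceed one half. Non-response lowers the effective bar further. The pass probabilities (0.82 to 0.92 as written against 0.04 to 0.01 as stated, at 40% true uptake) rest on an assumed 60 to 120 clients offered and full response. They describe the uptake criterion, not the joint feasibility conclusion.

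**What to change.** In the Analytic Plan for Hypothesis 3, define uptake as the number who accepted the SSC invitation divided by the total number offered it, counting accepted, declined and no response. Keep the threshold at more than .5. The attendance measure needs no change. Reporting the proportion with a 95% confidence interval would suit the stated interest in precise estimates, but the contradiction is resolved without it.

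The cost is one sentence of SAP wording and a count of offers made. The sample size does not change. The reported uptake figure will be lower than the ratio now specified.

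### Hypothesis 6 assigns a t test of unstated variance form to a yes/no outcome; a test for two proportions should be named (minor)

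*SAP*

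**What the plan says.** In the SAP's Analytic Plan, the Hypothesis 6 paragraph reads "we will conduct two 2-tailed independent-samples t tests". The first is described as follows: "we will assess whether the percentage of individuals removing themselves from the clinic's waitlist after completing the SSC differs from the percentage" among earlier clients. The second compares mean numbers of psychotherapy sessions. The rule for the first test is "A difference with a p value of < .05, with a higher value for the SSC group", which is read as a suggestion that SSC clients may be more likely to leave the waitlist.

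The same section adds a Benjamini-Hochberg step: "Results will be considered significant if FDR corrected q < 0.05". It applies that step to p values from t tests.

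On size, the Sample Size Justification gives "A client sample size of 40 from two outpatient sites". For the comparison group the Analytic Plan says only that "we will restrict our sample of previously-seen clients to those in the same age-range as in the study sample". No historical sample size and no removal rate is stated. Study Aims and Hypotheses describes the historical data for Hypothesis 6 with the words "which requires extraction of aggregate client information associated with previous" clients.

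**The concern.** Each client contributes a 0 or a 1 to the first comparison: left the waitlist or did not. The usual test for two such percentages is chi-square, Fisher's exact test or an equivalent, and the SAP names none of these. It names a test for means and leaves the variance form open.

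The open form matters because the two versions treat 0/1 data differently when the groups are unequal. The equal-variance form pools the two variances. The Welch form estimates each separately, and a group with no events then has an estimated variance of zero. The same data can therefore give different verdicts depending on the analyst's choice or a software default. The Hypothesis 6 data are also the last to be collected, possibly after Hypotheses 1 to 5 have been reported, so the choice should be closed in advance. The p value decides half of Hypothesis 6 and also enters the false discovery rate calculation, where it can shift other q values.

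**Working it through.** **No plan figure to reproduce.** The sample of 40 rests on pilot-study guidelines. The SAP gives no power, effect size, removal rate or comparison-group size for Hypothesis 6. The only error-rate figure is the two-sided .05 level.

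**Inputs.** SSC group n1 = 40 (SAP, an upper limit for this comparison). Alpha .05 two-sided (SAP). Historical n2 from 20 to 200 and removal rates from 2% to 50% (assumed).

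**Formulas**, with a = x/n1, b = y/n2 and s² = p(1−p)n/(n−1) in each group:
- Welch: t = (a−b)/√(s1²/n1 + s2²/n2), with Satterthwaite degrees of freedom.
- Equal variance: t = (a−b)/√[sp²(1/n1 + 1/n2)], with sp² = [(n1−1)s1² + (n2−1)s2²]/(n1+n2−2).
- Pearson: z = (a−b)/√[p̄(1−p̄)(1/n1 + 1/n2)], with p̄ = (x+y)/(n1+n2).

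**Two example tables (40 versus 100 clients).**
- *0/40 versus 4/100.* s1² = 0. s2²/n2 = 0.04 × 0.96/99 = 0.000388, with square root 0.0197. Welch t = −0.04/0.0197 = −2.03 on 99 df, p = .045. The equal-variance t gives p = .20 and Pearson p = .20. Only Welch rejects, and it points against the SSC.
- *6/40 versus 4/100.* s1²/n1 = 0.15 × 0.85/39 = 0.00327. Welch t = 0.11/√(0.00327 + 0.000388) = 1.82, p = .075. For equal variance, sp² = (5.10 + 3.84)/138 = 0.0648 and t = 0.11/√(0.0648 × 0.035) = 2.31, p = .022. Pearson p = .022. Only Welch misses a difference in favour of the SSC.

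**Exact type I error.** This sums the two binomial probabilities over every table with p < .05. Undefined tests count as non-rejections.

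| n2 | Common rate | Equal-variance t | Welch t | Welch, SSC rate higher |
|---|---|---|---|---|
| 100 | 5% | 4.1% | 10.3% | 0.48% |
| 200 | 5% | 4.2% | 13.4% | 0.35% |
| 200 | 3% | 3.8% | 25.4% | 0.16% |
| 150 | 2% | 3.0% | 15.8% | 0.09% |
| 150 | 5% | 4.0% | 12.8% | 0.40% |
| 150 | 10% | 4.6% | 6.9% | 0.84% |
| 80 | 5% | 3.6% | 8.7% | 0.85% |
| 40 | 5% | 4.3% | 3.8% | 1.9% |

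The nominal rate for the last column is 2.5%. In the first three rows, tables with no removals in the SSC group contribute 9.5, 12.7 and 25.2 points of the Welch total.

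Over n2 = 20, 40, 80 and 150 and rates of 2% to 50%, the equal-variance t and Pearson chi-square both run from 0.7% to 5.9%. They differ by at most 0.4 points in any of those cells, and by about 0.45 points (4.09% against 4.54%) at n2 = 100 and 5%.

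**Power in the hypothesised direction.**

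| SSC vs historical rate | n1 vs n2 | Equal-variance t | Welch t |
|---|---|---|---|
| 20% vs 5% | 40 vs 100 | 77.0% | 59.8% |
| 30% vs 10% | 40 vs 150 | 85.8% | 75.1% |
| 30% vs 10% | 40 vs 40 | 63.2% | 63.1% |

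Pearson chi-square matches the equal-variance column in all three rows. For 30% versus 10% with 40 versus 150, Fisher's exact test has power 82.3%.

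**The case against.** The strongest reply is that an unqualified independent-samples t test may well mean the equal-variance form. On 0/1 data that form is nearly the same test as Pearson chi-square, so the wording would be unconventional but harmless. That stands for the equal-variance form. It does not settle the matter, because the SAP does not say which form applies.

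A second reply is that the large Welch figures need three things at once: the Welch form, removals of about 5% or less, and a much larger historical group. This also stands. With n2 = 60 and a 5% rate, Welch is at 5.7%. With n2 = 60, 100 or 200 and rates of 20% or 30%, it lies between 5.2% and 5.8%.

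Two stronger readings are tempting, and the documents support neither.
- A reader might infer that any t test on this outcome has a distorted error rate. The equal-variance results show otherwise.
- A reader might infer that 10% to 25% is the chance of wrongly crediting the SSC. The SAP draws its conclusion only when the SSC rate is higher, and in that direction Welch rejects in under 1% of null datasets in every unequal-group row shown. The excess is a spurious unfavourable signal.

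A reader might also want a logistic model adjusted for site and age. The SAP plans no adjustment beyond matching the age range and describes the historical data as aggregate, so the absence of such a model is not an error here.

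**Conclusion.** The point holds in a limited form. The SAP assigns a test for means to a yes/no outcome and leaves its variance form open. If the equal-variance form is used, the effect is negligible. If Welch is used with a much larger historical group and uncommon removals, two-sided type I error is about 10% to 25% (100 to 200 historical clients, rates of 3% to 5%), nearly all towards a lower SSC rate. The cost in the direction the SAP acts on is lost power: 17.2 points (77.0 − 59.8) and 10.7 points (85.8 − 75.1) in the two unequal-group scenarios. All of this assumes 40 SSC clients with data and rests on assumed historical sizes and removal rates.

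Severity is minor. The SAP labels the Hypothesis 1 measures as primary, not Hypothesis 6, and words the Hypothesis 6 conclusion cautiously.

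**What to change.** In the Hypothesis 6 paragraph, replace the first t test with a named test for two proportions: Pearson chi-square, or Fisher's exact test when expected counts are small. Report the risk difference with a Newcombe 95% confidence interval. Keep the t test for number of sessions only. In the false discovery rate paragraph, widen the reference to p values from t tests so that this p value stays in the set.

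The cost is two wording edits and no new data. Counts and denominators are enough, so aggregate historical data suffice. The downside is that Fisher's test is somewhat conservative: its type I error never exceeded 4.1% over the grid of n2 from 20 to 150. It gives up 3.5 points of power against chi-square (85.8 − 82.3) for 30% versus 10% with 40 versus 150 clients.

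### The first Hypothesis 6 test compares raw self-removal percentages with no allowance for time at risk, so a difference in waiting or observation time between periods can look like, or hide, an SSC effect

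*SAP*

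**What the plan says.** Aim 6 is "To assess rates of (a) remaining on the clinic waitlist for therapy", relative to clients who sought services "in the six months prior to the SSC being offered to clients (January June 2019"). Hypothesis 6 predicts: "Clients who receive the SSC will be less likely to remain on the clinic wait list".

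The Analytic Plan implements this with a two-sided independent-samples t test: "we will assess whether the percentage of individuals removing themselves from the" waitlist differs between the two groups. The SSC figure is the share of clients who take themselves off the list after completing the SSC, with no end date. The comparator is the "percentage of individual who had removed themselves from the waitlist in the six months prior to the" SSC. A significant result with the higher value in the SSC group "would suggest that individuals who receive the SSC may be more likely to voluntarily remove themselves from the clinic waitlist" than earlier clients were.

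The second test counts psychotherapy sessions "among individuals who receive the SSC and elect to remain on the" waitlist. A client who went on to therapy is thus in the group that remained.

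The only comparability step is restriction to the same age range. The Study Timeline projects SSC recruitment from October 2019 to about May 2020. The SAP states no denominator for the percentages, no common follow-up and no waiting times, and does not say how an exit into therapy is handled in the first test.

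**The concern.** A client can leave the list by self-removal or because therapy starts, and therapy start ends the opportunity to self-remove. A simple percentage therefore reflects two things: how readily clients leave, and how long they were at risk of leaving. The second depends on clinic capacity in each calendar period and on how long each group is observed. Age restriction addresses neither.

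Observation time is unequal on the face of the text. SSC removals are open-ended. Past removals are, on a literal reading, those that fell within the six months, so a client listed late in that period would be observed only briefly.

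The pre-stated interpretation credits the SSC with any significant excess of self-removal. It could be credited with an effect of longer waits or longer observation, or a real effect could be cancelled by shorter waits. The false discovery rate step adjusts p-values for multiplicity and does not remove bias.

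**Working it through.** The SAP gives no figure to reproduce for this test: no removal rate, waiting time or historical sample size. The check asks what the planned comparison shows when the SSC has no effect.

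**Inputs.** From the SAP: 40 SSC clients, two-sided t test, p < .05. Assumed: a constant self-removal rate λ per month, equal in both groups; exponential waits until therapy with mean w months; 40 to 200 past clients.

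**1. Unlimited follow-up.** P(self-removal before therapy) = λ / (λ + 1/w).

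| λ per month | w = 2 | w = 4 | Difference |
|---|---|---|---|
| 0.05 | 0.05/0.55 = 9.1% | 0.05/0.30 = 16.7% | 7.6 points |
| 0.10 | 0.10/0.60 = 16.7% | 0.10/0.35 = 28.6% | 11.9 points |
| 0.15 | 0.15/0.65 = 23.1% | 0.15/0.40 = 37.5% | 14.4 points |

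At λ = 0.10 and w = 3 the value is 0.10/0.4333 = 23.1%.

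**2. Common window of t months.** P = [λ / (λ + 1/w)] × [1 − exp(−(λ + 1/w)t)], with λ = 0.10.

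| t (months) | w = 2: 0.1667 × (1 − e^(−0.6t)) | w = 4: 0.2857 × (1 − e^(−0.35t)) | Difference |
|---|---|---|---|
| 1 | 7.5% | 8.4% | 0.9 points |
| 2 | 11.6% | 14.4% | 2.7 points |
| 3 | 13.9% | 18.6% | 4.7 points |
| 6 | 16.2% | 25.1% | 8.9 points |

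A short common window removes most of the distortion; a six-month window leaves much of it.

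**3. Unequal observation, equal waits.** With λ = 0.10 and w = 3 in both groups, open-ended follow-up gives 23.1%. A past client listed halfway through the six months, and counted only if removal falls within them, has 3 months: 0.2308 × (1 − e^(−1.3)) = 16.8%. That is a 6-point gap with neither an SSC effect nor a change in waits.

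**4. Effect on the planned test.** The pooled t test on 0/1 outcomes was simulated with no SSC effect, λ = 0.10, unlimited follow-up, fixed or exponential waits, and 40 v 40, 100 or 200 clients. The proportion of trials significant in the SSC's favour (nominal 2.5%) was:

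- waits 3 v 3 months (SSC v past): about 2 to 3%
- 4 v 3 months: 8 to 16%
- 4 v 2 months: 25 to 56%
- 6 v 3 months: 28 to 67%

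With waits of 1.5 v 3 months, 21 to 35% of trials were significant against the SSC.

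**5. Rate comparison.** Self-removals per person-month on the list, with therapy start ending time at risk, gave 0.0999 v 0.1000 per month for waits of 6 v 3 months. Two-sided rejection was 3.6% to 5.0% over four scenarios.

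**6. Where the clock starts.** SSC clients cannot have a counted removal before their SSC. Suppose the SSC is one month after listing, λ = 0.10 and w = 3. Mean time at risk after the SSC is 1/0.4333 = 2.31 months. Counting the month before it as well gives 3.31, and the apparent rate ratio under no effect is 2.31/3.31 = 0.70. An analysis from listing without delayed entry would replace one bias with another.

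**The case against.** **Endpoint mismatch.** A reader might infer that the hypothesis (remaining) and the test (self-removal) address different endpoints. The document does not support that. Hypothesis 6 goes on to speak of those who choose to stay, so remaining is used as the opposite of choosing to leave, and a therapy starter did choose to stay. The mismatch in wording is mild and is not the point here.

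**Inference.** No sentence says that therapy starters are non-removers in the first test; this follows from the group used in the second. The objection stands as a caution. Excluding therapy starters would not help, because the percentage would still depend on how long the others waited.

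**Conditional size.** Nothing in the SAP shows that waits changed. The 12-point figure needs a doubled wait, a constant monthly rate and unlimited follow-up. If clients decide soon after the session, the dependence on waiting time shrinks. This stands.

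**A common window might suffice.** A short one largely would, as step 2 shows. But the SAP sets no common window, and a longer one leaves a material difference.

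**Stakes.** The primary outcomes are hope and agency, the study is a pilot of 40, and the conclusion is worded cautiously. This limits the priority. It does not make the comparison sound.

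**Conclusion.** The point holds. As written, the first Hypothesis 6 test confounds any SSC effect with differences between periods in waiting time and observation time, and age restriction does not address either. This goes beyond missing detail, because following the stated rule can give a wrong answer.

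A reader might go further and conclude that the result will be biased in the SSC's favour, or by about 12 points. The SAP does not support that: it gives no waiting times or removal rates, so direction and size are unknown. Under an assumed 10% per month self-removal with exponential waits, 4 v 2 months gives 28.6% v 16.7% with unlimited follow-up, and a difference of 0.9 to 4.7 points within a common window of 1 to 3 months. A longer wait in the SSC period would favour the SSC; a shorter one would work against it.

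The change should be made, but it concerns a secondary, exploratory question.

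**What to change.** Replace the raw-percentage t test with a comparison of self-removal over time at risk:

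- Define the same denominator and a common maximum follow-up in both groups.
- Take the listing date as time origin, with SSC clients entering the risk set only at their SSC date (delayed entry), so that no immortal time is credited to the SSC group.
- Treat therapy start as a competing exit: censor at it for the cause-specific rate or hazard comparison, and show cumulative incidence of self-removal alongside.
- Extract listing, self-removal and therapy-start dates for all clients, and the SSC date for SSC clients.

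The SAP defers collection of Hypothesis 6 data until all therapy courses have ended, so the analysis can be respecified before anyone sees them.

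**Cost.** The SAP plans aggregate information on past clients; this needs client-level dates, which the clinic records are assumed to hold. The age restriction and the session-count comparison already draw on individual records, so the extra work should be modest. The estimate will be imprecise: at 16.7% to 28.6% self-removal, 40 SSC clients give about 7 to 11 events. Other differences between the periods remain, so the result should be reported as exploratory.
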